6.0 Enrollment

We intend to enroll twenty-five evaluable Carevix subjects prior to commencing the enrollment of the control-group tenaculum subjects. An additional five Carevix subjects (for a total of N=30) will be concurrently enrolled while accruing the thirty additional tenaculum subjects for a total enrollment of N=60.

7.0 Study Procedures

Any intrauterine procedure already scheduled will otherwise proceed accordingly as part of clinical care. During the enrollment, patients who fit above inclusion criteria and are scheduled for an intrauterine procedure may be offered the opportunity to participate in this program and trial the new Carevix[™] device during the exposure recruitment period and complete a short survey. If the patient consents to the use of Carevix[™] Ambassador program, the suction-based cervical stabilizer will be used on their cervix to stabilize the cervix during the procedure instead of the traditional tenaculum. If the patient or provider opts out of the use of Carevix[™], they will be asked if they'd like to participate in the study with the tenaculum. During the tenaculum enrollment phase, patients will receive the standard of care device and complete a short survey.

Following completion of the procedure, the patient will then fill out the patient-based survey. Following the completion of the patient's questions, the provider will then fill out the provider-based survey.

The questionnaire for the Carevix[™] Ambassador program will be stored within the Aspivix company database (all questions are HIPAA compliant and do not reveal PHI). The survey is labeled as originating from Indiana University for easy access to only our patient data.

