4.0 Eligibility Criteria

4.1 Inclusion Criteria (to be assessed prior to procedure)

- Age 18 years or older
- Speaks and reads in English
- Able to consent on their own
- Will undergo any intrauterine procedure using the Carevix[™] (for exposure group) or using Tenaculum (for Control Group)
- Up to 20 providers performing this procedure
- Provider is willing to use Carevix[™] for scheduled procedure

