4.2 Exclusion Criteria (to be assessed by provider at time of procedure)

- Vaginal bleeding of unknown origin
- Cervix less than 26 mm in diameter
- Nabothian cyst on anterior lip of cervix
- Cervical myomas
- Cervical abnormalities/shape
- Pregnant

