5.0 Study Design

Aspivix, the company that created Carevix[™], launched the Ambassador Program, a 3-6 month program with free of charge devices for clinics willing to test Carevix[™] in multiple intrauterine procedures. Our clinic, Coleman Center, will conduct a prospective cohort study for 3-6 months where patients who qualify via inclusion criteria who are also receiving an intrauterine procedure (endometrial biopsy, IUD insertion, manual aspiration, etc) on the exposure (Carevix[™]) arm will have the opportunity to receive the Carevix[™] device for cervical stabilization, per provider preference (i.e., providers may decline to use Carevix[™] for endometrial biopsy).

Once 25 participants have received Carevix[™], recruitment for the control (tenaculum) arm will begin. Participants will receive the standard of care device if cervical stabilization is required. Each participant will be provided with a study information sheet and sign a consent form. They will then undergo their planned procedure, using the assigned device.

Following completion of their procedure, they will also agree to fill out a survey about their experience, which takes about 1 minute to complete. The provider performing the procedure will finish the survey with provider-specific questions about bleeding, ease of use and satisfaction. The purpose of this study is to compare Carevix[™] to the tenaculum and determine if the Carevix[™] shows similar results in the United States population as it has in the European study and with all intrauterine procedures.

*Once 25 of 30 patients received CarevixTM, will commence control group collection N = 30

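### Sections 4.1, 4.2, 7.0 and 11.0 do not settle whether patients whose provider declines Carevix, or who are unsuitable for it, belong in the control arm

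*Combined protocol and SAP*

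**What the plan says.** Section 4.1 is headed "Inclusion Criteria (to be assessed prior to procedure"). Its last item is "Provider is willing to use Carevix[™] for scheduled procedure", with no arm named. The fourth item in the same list does separate the arms ("for exposure group) or using Tenaculum (for Control Group").

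Section 4.2 is one list, headed "Exclusion Criteria (to be assessed by provider at time of procedure"), and is not restricted to either arm.

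Section 5.0 makes use of the device a matter of provider preference and gives an example: "providers may decline to use Carevix[™] for endometrial biopsy". On timing it says "Once 25 participants have received Carevix[™], recruitment for the control (tenaculum) arm will begin". Section 6.0 agrees: 25 evaluable Carevix patients come "prior to commencing the enrollment of the control-group tenaculum subjects", and the last five Carevix patients are enrolled alongside the 30 controls.

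Section 7.0 says that, when the patient declines or the "provider opts out of the use of Carevix[™], they will be asked if they'd like to participate in the study with the tenaculum". It does not refer back to the enrolment order in 5.0 and 6.0.

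Section 11.0 covers patients who consented to Carevix but need no stabilization or are judged unsuitable for the device. It calls them ineligible on condition that they do not receive the tenaculum, with an exception for those who consented to it.

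Section 12.0 plans standard tests, with chi-square and t-tests as examples, for baseline characteristics and similar testing for outcomes.

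**The concern.** A patient whose provider refuses Carevix appears to fail 4.1, yet 7.0 invites her into the tenaculum group. A patient excluded under 4.2, for example for cervical size or shape, may be kept as a control under 11.0. Both routes run one way, because neither kind of patient can appear in the Carevix arm.

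Allocation is not randomized. Refusal may follow the type of procedure, and unsuitability may follow cervical anatomy. Either could be related to pain or bleeding, in either direction. Section 12.0 describes no adjustment and no analysis by entry route, and the visible text describes no field that records the route. Two coordinators could reasonably enrol different patients as controls, and a reader of the results could not tell who had been compared.

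**Working it through.** **1. Provider opt-out: 4.1 against 7.0.** The two sections agree under either of two readings:
- the provider was willing when 4.1 was assessed, before the procedure, and opted out later;
- the willingness item applies to the Carevix arm only.

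The visible text states neither. A patient's own opt-out does not conflict with 4.1.

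**2. Device-ineligible patients: 4.2 against 11.0.** Section 11.0 does not waive 4.2. However, its condition about receiving or consenting to the tenaculum suggests that some of these patients stay in the study, and control is the only arm left for them.

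**3. How many opt-outs can become controls.** Sections 5.0 and 6.0 open control enrolment after the 25th Carevix patient, so opt-outs after a Carevix offer can become controls only while the last five Carevix patients enrol. Assume that a proportion p of patients offered Carevix opt out and that all of them join as controls. The number of opt-outs before the fifth acceptance is then negative binomial with mean 5p/(1 − p). Six or more opt-outs means at most four acceptances in the first ten offers.

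| Assumed p | Expected opt-outs | Chance of 6 or more |
|---|---|---|
| 0.2 | 5 × 0.2/0.8 = 1.25 | 0.6% |
| 0.4 | 5 × 0.4/0.6 = 3.3 | 17% |
| 0.5 | 5 × 0.5/0.5 = 5.0 | 38% |

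Put the other way, 3 routed patients means 3/8 = 38% of those offered Carevix opted out, and 6 means 6/11 = 55%. These counts include patient opt-outs, so for a given total refusal rate they overstate the provider opt-outs at issue.

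**4. Effect on the pain comparison.** The plan's 30 per group (80% power, two-sided 5%) cannot be reproduced, because 12.0 gives neither a difference nor an SD. With the t-test it corresponds to a standardized difference of 0.736, or 0.736 × 25 = 18.4 mm at an assumed SD of 25 mm on a 100-mm scale.

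Let k of the 30 controls differ in mean pain by an assumed gap. The bias in the mean difference is k × gap/30. With a 20 mm gap this is 3 × 20/30 = 2 mm for k = 3 and 6 × 20/30 = 4 mm for k = 6. The standard error is 25 × √(2/30) = 6.5 mm.

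Simulated type I error with no device effect (200,000 trials per case, normal scores, pooled t-test with 58 df, gap added to k individual controls; 5.0% at k = 0):

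| Routed controls | 10 mm gap, SD 25 | 20 mm gap, SD 25 | 20 mm gap, SD 30 to SD 20 |
|---|---|---|---|
| 3 | 5.1% | 5.7% | 5.6% to 6.0% |
| 6 | 5.9% | 8.5% | 7.5% to 10.4% |

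If the routed controls instead have 20 mm less pain and the true benefit is 18.4 mm, power falls from 80% to about 69% with 3 and 57% with 6.

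**5. What cannot be counted.** The documents do not allow an estimate of the number of device-ineligible patients kept. Nor do they allow one for ordinary controls in the tenaculum phase whose provider would have declined Carevix, a group that exists if the 4.1 item is Carevix-only. The window in step 3 does not cap that second group.

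**The case against.** The strongest reply is that this is a missing label and not a contradiction. Section 4.1 is assessed before the procedure and 4.2 during it, so a later opt-out is compatible with earlier willingness. Section 5.0 places provider preference under the exposure arm. The 4.1 list also contains a study-level item (the cap on providers), so its arm labels are weak evidence of intent. Section 11.0 is one badly drafted sentence that also covers patients needing no stabilization, whom 4.3.1 makes ineligible in either arm. A figure directly after 4.3.1, the questionnaire, the consent form and the RedCap fields are not shown and may settle the routing. Finally, 12.0 does plan to compare descriptive characteristics.

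Much of this stands. A reader might infer that 4.1 and 7.0 cannot both hold, or that 11.0 waives 4.2. The text supports neither inference. What remains is that the visible text leaves the choice of reading open and that 7.0 expressly describes a one-way route. A baseline comparison can reveal an imbalance but does not correct it.

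A reader might also infer that many controls are affected. Twelve routed controls with a 20 mm gap at SD 25 would raise type I error to 20.7%, but 12 opt-outs from the enrolment window would need 12/17 = 71% of patients offered Carevix to opt out. The documents give no ground for assuming that.

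**Conclusion.** The concern holds as an unresolved eligibility and routing rule that can bias the pain and bleeding comparisons, in a direction the documents do not reveal. It should be fixed, with medium confidence. An inference that the bias favours Carevix would go beyond the text, since routed patients may have more or less pain than other controls.

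For opt-outs the effect is probably small. Inflation is negligible at about 3 routed controls and modest at 6, and 6 would require common refusal in the window. All these figures rest on an assumed SD, gap and number routed. The scope of the 4.1 item may matter more than the opt-outs, because if it is Carevix-only the number of ordinary controls whose provider would have declined the device has no cap.

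**What to change.** - Reconcile 4.1, 4.2, 5.0, 7.0 and 11.0: state which inclusion and exclusion criteria apply to which arm and who is retained under 11.0. Cross-refer 7.0 to the enrolment order in 5.0 and 6.0.
- Record in RedCap, before the procedure, whether the provider would accept Carevix. It is a judgement and cannot be reliably reconstructed afterwards. Also record the entry route: standard control, provider opt-out, patient opt-out or device-ineligible.
- In 12.0, base the primary comparison on patients in both arms who meet the same 4.1 and 4.2 criteria. Report provider opt-outs and device-ineligible patients separately, with their number.
- If the sponsor prefers to keep the 7.0 route in the primary analysis, pre-specify a sensitivity analysis without those patients.

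The cost is rewording in a few sections, one or two data fields and slightly slower control accrual, by an amount the documents do not allow to be estimated. The primary comparison would also cover only procedures for which the provider would accept Carevix, which is narrower than the stated aim of all intrauterine procedures. The other confounding of a non-randomized, mainly sequential cohort remains. The change concerns who is compared, not which device a patient receives.

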8.0 Study Calendar

There is no study calendar – the patient will have their intrauterine procedure scheduled and will decide if they wish to participate in the Carevix[™] Ambassador program or not. The event will be a one-time procedure only when the Carevix[™] suction-based cervical stabilizer is used or the tenaculum is used.

9.0 Reportable Events

It is not anticipated that there will be Serious Adverse Effects as defined by the FDA (death, lifethreatening complications, need for hospitalization, disability or permanent damage, or an intervention needed to prevent permanent impairment or damage). However, if one occurs, it will be promptly reported to the IU IRB and sponsor (within 5 days of knowing about the occurrence) and per IU HRPP policy if unexpected, related/possibly related to participation and if the SAE suggests that the research places the subject or others at greater risk of harm.

Other adverse events (AE) that may occur with any cervical stabilization device, such as bleeding or injury at stabilization site needing medication or surgical intervention, are common and will be collected and reported as part of study data and at annual regulatory reviews.

10.0 Data Safety Monitoring

This study is no greater than minimal risk. Data safety and monitoring will be performed by the database manager for the Qualtrics database and the PI. Data quality, subject recruitment data completion, outcome and adverse event data, and proper consent procedures will be regularly reviewed by the PI, study coordinator, and data manager at least monthly. A formal Data Safety Monitoring Board is not required. While no formal stopping criteria are proposed, monitoring of AEs will be ongoing and will be discussed by the PI and Department representatives if the AE rate (notably bleeding or injury to the stabilization site on the cervix) is above 50%.

11.0 Study Withdrawal/Discontinuation

Patients can decline participation and will receive standard of care if cervical stabilization is required. Patients who consent to receiving the Carevix[™] and who require no cervical stabilization or is assessed by the provider to be otherwise ineligible for the device will be considered ineligible if they do not receive tenaculum (unless consented for tenaculum) and will not be required to complete any surveys or follow-ups.

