12.0 Statistical Considerations

We performed sample size/power calculations with the primary outcome of pain (visual analog scale) at the time of Carevix[™]/tenaculum use. Thirty participants per group (total N=60) are needed to achieve at least 80% power and a two-sided 5% significance level. Descriptive characteristics of those in the Carevix[™] and control groups will be compared using standard statistical testing such as Chi-square and t-tests. Differences in outcomes between the device and control groups will similarly utilize standard testing.

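### Carevix-consented patients can leave the Carevix arm according to the device they end up receiving, and no rule says how a Carevix attempt completed with a tenaculum is analysed

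*Combined protocol and SAP*

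**What the plan says.** The study is a non-randomised comparison. Section 5.0 says the clinic "will conduct a prospective cohort study for 3-6 months where patients who qualify via inclusion criteria" take part, with Carevix used according to provider preference and each procedure done "using the assigned device". Five places bear on which group a patient ends up in.

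- **Section 4.2** lists exclusions that the provider assesses at the procedure, such as a cervix under 26 mm, a Nabothian cyst on the anterior lip, or cervical abnormalities/shape. It does not limit them to one arm.
- **Section 6.0**: "We intend to enroll twenty-five evaluable Carevix subjects" before control enrolment opens. The meaning of evaluable is not given.
- **Section 7.0**: if the patient or the provider opts out of Carevix, the patient is asked whether they would "like to participate in the study with the tenaculum".
- **Section 11.0** covers Carevix-consented patients who need no stabilisation, or who are judged "otherwise ineligible for the device will be considered ineligible if they do not receive tenaculum (unless consented for tenaculum"). It does not say which group a patient joins if a tenaculum is then used.
- **Section 12.0** sets the size ("Thirty participants per group (total N=60) are needed to achieve at least 80% power and a two-sided 5% significance level") and the analysis ("Differences in outcomes between the device and control groups will similarly utilize standard testing"). It defines no analysis population.

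**The concern.** Two things follow from these sections.

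First, a patient found unsuitable for Carevix at the procedure, or whose provider opts out, leaves the Carevix arm and may be kept as a tenaculum subject. If the reason is a Section 4.2 condition, such patients can then appear in the control arm but not in the Carevix arm. That makes the groups differ by cervical anatomy.

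Second, neither the ineligibility wording nor the opt-out wording says whether the decision must come before suction is applied. A Carevix attempt that is abandoned and completed with a tenaculum could be kept in the Carevix arm, dropped as not evaluable, or counted as tenaculum. The choice could be made after the outcome is known. Converted patients experience both instruments, so their pain and bleeding may well differ from the rest. They are also the most informative cases for the secondary objective of ease of use. With 30 per arm, three such patients are enough to move the result.

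**Working it through.** **The plan's own figure.** The calculation in Section 12.0 is described as "sample size/power calculations with the primary outcome of pain (visual analog scale) at the time of" device use, but no difference or SD is stated, so 30 per group cannot be reproduced forwards. Solved backwards, the standardised difference detectable with 80% power at two-sided 5% is (1.960 + 0.842) × √(2/30) = 0.72 SD, or 0.74 SD with the t distribution. At an assumed SD of 25 mm, 0.72 SD is about 18 mm.

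**Inputs.** From the documents: 30 per group, two-sided 5%. Assumed, because the documents give none of them: SD 25 mm, conversion fraction f = 10% or 20%, and converted patients scoring e = 20 or 30 mm higher than non-converted Carevix patients. There is no true difference by first device: the tenaculum mean is set at 0, Carevix successes at −f·e and conversions at (1 − f)·e, so that all Carevix attempts together average 0.

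**Formulas (Carevix minus tenaculum; negative favours Carevix).**
- Kept: 0.
- Dropped: −f·e.
- Moved: Carevix mean −f·e. Control mean 30f(1 − f)e / (30 + 30f) = f(1 − f)e/(1 + f). Difference −2f·e/(1 + f).

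**Numbers.**
- f = 10%, dropped: 0.1 × 20 = 2 mm to 0.1 × 30 = 3 mm.
- f = 10%, moved: 2 × 0.1 × 20/1.1 = 3.6 mm to 2 × 0.1 × 30/1.1 = 5.5 mm.
- f = 20%, dropped: 4 to 6 mm.
- f = 20%, moved: 2 × 0.2 × 20/1.2 = 6.7 mm to 2 × 0.2 × 30/1.2 = 10 mm.

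Pooled two-sample t-tests were simulated (40,000 runs per case) under the same assumptions. The table shows the chance of falsely declaring Carevix better.

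| Conversion | Kept | Dropped | Moved |
|---|---|---|---|
| 10% | about 2.5% | 5-7% | 8-12% |
| 20% | about 2.5% | 8-14% | 16-29% |

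**Reverse direction.** If converted patients score 20 mm lower, the shifts keep their size and change sign. At 10% conversion the chance of falsely declaring Carevix worse becomes about 5% (dropped) or 8% (moved).

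**Device-ineligible patients in control only.** If 3 of the 30 control patients were of this kind and scored 20-30 mm higher, the control mean would rise by (3/30) × 20 = 2 mm to (3/30) × 30 = 3 mm. The count and the excess are again assumptions.

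**The case against.** The strongest reply is that no section mentions a failed or abandoned Carevix attempt. Section 11.0 deals with patients who need no stabilisation and patients ineligible for the device, and ineligibility most naturally means the Section 4.2 conditions. In Section 7.0 the opt-out follows the consent step and reads as declining Carevix beforehand. Section 5.0 counts participants who have received Carevix and refers to the assigned device, which would support keeping a failed attempt in the Carevix arm. Control enrolment opens only after 25 Carevix participants, which limits moves to control, although the Section 7.0 offer is not tied to that phase.

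All of this stands as a limit on the claim. A reader might infer that the plan directs Carevix failures out of the Carevix arm, and that the comparison therefore favours Carevix. The documents do not support that: keeping failures is an equally open reading, and nothing shows whether converted patients fare worse. Nor can one infer that the survey completed fixes the group. Section 13.0 holds the two arms' data in separate systems, but no text says which form a patient with both devices completes, and the questionnaire is not available for review.

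It is also fair that analysis by first device protects no randomisation here, and that bleeding after conversion may be due to the tenaculum. These are reasons for a sensitivity analysis. They do not supply the missing rule, and they do not explain why Section 11.0 makes status depend on receiving a tenaculum when the Section 4.2 exclusions apply to the study as a whole.

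**Conclusion.** The concern holds in a limited form. Sections 7.0 and 11.0 tie a Carevix-consented patient's status to the device finally received, which sits badly with Section 4.2 and can place device-ineligible patients in control only. For conversions, no analysis group is stated and the wording does not prevent keeping, dropping or moving them. The direction of bias is conditional: towards Carevix if converted patients do worse, against it if they do better.

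Under the assumptions shown, the false benefit is 2-5.5 mm at 10% conversion and 4-10 mm at 20%. Against the detectable difference of about 18 mm, that is roughly 11-30% and 22-55%. These figures illustrate sensitivity and do not estimate what will happen, because conversion rate, excess pain and SD are all assumed. The point should be settled before analysis, since the remedy is cheap and the choice could otherwise be made with the outcomes in view.

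**What to change.** - State in Sections 11.0 and 12.0 that the primary analysis group is the first device applied to the cervix. Any Carevix attempt stays in the Carevix arm, completes the survey and counts as evaluable, even if a tenaculum follows. Define evaluable in Section 6.0 accordingly.
- Record conversion (yes/no, with reason) in both arms and report it by arm.
- Reconcile Section 11.0 with Section 4.2, so that patients found to meet a 4.2 exclusion before any device is applied are left out of the comparison in both arms. State in Section 7.0 whether an opt-out can follow an attempt.
- Add a sensitivity analysis by device finally used, or one excluding conversions.

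The cost is wording and one conversion item, which can be recorded in RedCap if the company's survey cannot be changed. The Carevix result may look less favourable. These changes concern analysis groups and do not alter which device a provider uses.
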